12.5.1.1 Sensitivity Analyses

The primary endpoint will be also analyzed for mITT and PP using the same continuous Repeated Measure Model described in [Section 12.5.1](#).

In addition, there will be a sensitivity analysis accounting for the individual pain scores influenced by the protocol-prohibited concomitant medications. In this analysis, the pain scores after receiving protocol-prohibited concomitant medication will be replaced with the baseline value only if a prohibited medication was used during the 10 days prior to Day 90 visit, Day 180 visit, Day 270 visit or Day 365 visit.

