9.2.3. Modified ITT Population

The modified ITT (mITT) population includes all Participants who meet the following:

- Underwent (any) injections (Engensis or Placebo) in Study VMDN-003-2
- Correctly completed the BPI-DPN eDiary at Baseline and the 12-month follow-up in Study VMDN-003-2b

Participants will be grouped based on the randomly assigned treatments, not the actual treatment received. The mITT population will be used in the sensitivity analyses for the primary and secondary efficacy endpoints.

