9.3 Modified Intent-to-Treat (mITT) Population

The modified ITT (mITT) population includes all participants that meet the following:

- Underwent (any) injections in Study VMDN-003-2
- Correctly completed the BPI-DPN eDiary at Baseline and the 12-month follow-up (with at least 5 of 7 days of BPI-DPN eDiary collected prior to Day 365 Visit) in Study VMDN-003-2b. Participants will be grouped based on the randomly assigned treatments, not the actual treatment received. The mITT population will be used in the sensitivity analyses for the primary and secondary efficacy endpoints.

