9.4 Per Protocol (PP) Populations

The Per Protocol population is a subset of mITT. It includes all mITT participants who meet all of the following criteria for Study VMDN-003-2 and Study VMDN-003-2b:

- The participant meets major protocol eligibility criteria determined by Clinical Data Review Committee (CDRC) prior to database lock and breaking the randomization codes.
- The participant received all 32 injections from each visit (Day 0, Day 14, Day 90 and Day 104) in Study VMDN-003-2, based on the randomized treatments and had a Day 365 Visit, including a 7-day ADPS (with at least 5 of 7 days of BPI-DPN eDiary collected prior to Day 365 Visit).

The CDRC, which is blinded to the treatment information of each participant, may determine additional criteria, if any, before unblinding the randomization code.

The PP population will be used in the sensitivity analyses for the primary and secondary efficacy endpoints.

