10.6.1 Missing Pain Scores for the Average Scores from BPI-DPN

The means of the Average Daily Pain Scores (Question 5 from the BPI-DPN) for a visit will be considered as missing if fewer than 5 of 7 days of BPI-DPN eDiary entries are provided. Any missing mean pain score of ADPS will be imputed using the methods described below.

Multiple Imputation (MI) method:

- Step 1: Intermittent missing values will first be imputed by treatment group using the Markov Chain Monte Carlo (MCMC) method, resulting in data with a monotone pattern.
- Step 2: Multiple imputation by treatment group using linear mixed model regression with factors of baseline pain score, baseline HbA1c, gender, and age at informed consent (Study VMDN-003-2) will be applied to the data obtained from the MCMC step. The imputed score will be rounded to the first decimal point.

The entire procedure will be repeated 10 times, and 10 complete datasets will be used for the analysis.

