12.5.2.3 Other Analysis of the Secondary Efficacy Endpoints

The secondary endpoints (not including PGIC endpoints) will be also analyzed for mITT and PP using the same analysis method described in Section 12.5.1. PGIC endpoint will be summarized by treatment group.

In addition, there will be a sensitivity analysis accounting for the individual pain scores influenced by the protocol-prohibited concomitant medications. In this analysis, the pain scores after receiving protocol-prohibited concomitant medication will be replaced with the baseline value only if a prohibited medication was used during the 10 days prior to Day 90 visit, Day 180 visit, Day 270 visit or the Day 365 visit.

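### No visible sensitivity analysis lets unobserved Day 365 pain scores depart from missing at random, and imputation Step 2 should name the earlier scores

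*SAP*

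**What the plan says.** SAP 10.6.1 treats a visit's mean ADPS as missing when fewer than 5 of 7 diary days are available, and imputes it in two steps within treatment group. Step 1 fills intermittent gaps by MCMC, "resulting in data with a monotone pattern". Step 2 is described as "Multiple imputation by treatment group using linear mixed model regression with factors of baseline pain score, baseline HbA1c, gender, and age at informed consent". SAP 12.5.1 then fits the repeated-measures model (Days 90, 180, 270 and 365) to each of 10 completed datasets and pools the results.

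SAP 12.5.1.1 lists the sensitivity analyses. First, "The primary endpoint will be also analyzed for mITT and PP using the same continuous Repeated Measure Model". Second, "pain scores after receiving protocol-prohibited concomitant medication will be replaced with the baseline value" if such a drug was taken in the 10 days before an analysed visit. The mITT set requires a completed diary at Day 365 ("with at least 5 of 7 days of BPI-DPN eDiary collected prior to Day 365 Visit", SAP 9.3), and "The Per Protocol population is a subset of mITT" (SAP 9.4).

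The protocol adds nothing further. Section 9.2.3 says "The mITT population will be used in the sensitivity analyses for the primary and secondary efficacy endpoints", and 9.2.4 says the same of PP. For the secondary endpoints SAP 12.5.2.3 repeats the pattern: "The secondary endpoints (not including PGIC endpoints) will be also analyzed for mITT and PP using the same analysis method".

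**The concern.** Imputing within arm from the scores that were seen assumes that participants who stop the diary would have scored like comparable participants in the same arm who continued. In an untreated six-month follow-up meant to test durability, returning pain is a plausible reason to stop. If that happens differently in the two arms, and the earlier scores do not show it, the Day 365 difference is biased in either direction, even when earlier scores are used for imputation.

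The planned runs say little about this. The participants in doubt are those without a Day 365 mean, and mITT and PP leave them out. A reader of the report could take agreement among ITT, mITT and PP as showing robustness to dropout, when no run had asked what happens if the unseen scores were worse, or better, than predicted.

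The Step 2 wording is a second, separable matter. If the four listed factors really are the only predictors, dropout that earlier ADPSs would explain is not adjusted for. mITT would then reproduce almost the same error instead of exposing it.

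**Working it through.** **Inputs.** The plan has no figure to reproduce. Protocol 9.1 refers sample size to the main study, and SAP 8.1 leaves N to whoever completes Day 180 and consents. From the documents: two-sided 0.05, 10 imputations, the 5-of-7 rule and the four visits. All SDs, correlations, effects and missing rates below are assumed.

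**1. What each run does with an unobserved Day 365 mean**

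| Run | Participants | Unobserved Day 365 mean |
|---|---|---|
| Primary | ITT, from Day 180 | imputed within arm, missing at random |
| mITT | observed Day 365 mean required | participant left out |
| PP | subset of mITT | participant left out |
| Prohibited medication | not restated | no rule given; changes scores after prohibited drugs |

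No row lets the unobserved value depart from its missing-at-random prediction.

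**2. What a departure is worth.** If imputed Engensis Day 365 scores are worsened by delta, and a share m of Engensis Day 365 means is imputed, the difference moves by m × delta. For delta = 1: 0.10 × 1 = 0.10, 0.20 × 1 = 0.20, 0.30 × 1 = 0.30. A simulation with 10 imputations, n = 50 and 100 per arm, and scores rounded to 0.1 and capped at 10 gave 0.094–0.097, 0.199 and 0.295–0.298.

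**3. How near the tipping point could lie.** Approximate crossing delta = (|z| − 1.96) × SE / m. With assumed z = 2.5, SE = 0.30 and m = 0.20: 0.54 × 0.30 / 0.20 = 0.81, under one point on the 0–10 scale.

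**4. Simulated Day 365 difference.** 200,000 per arm; SD 2; correlation 0.7 between post-baseline visits and 0.4 with baseline; assumed true difference −1.0; 20% Engensis and 10% Placebo missing. Dropout follows Day 270, with a slope of 1 logit per SD (0.5 per point). Day 365 ANCOVA on baseline stands in for the repeated-measures contrast.

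| Dropout driven by | Full data | mITT | Step 2, baseline pain only | Step 2 with earlier ADPS |
|---|---|---|---|---|
| Day 270 score (seen) | −0.996 | −1.085 | −1.086 | −0.995 |
| Day 365 score (unseen) | −0.995 | −1.134 | −1.129 | −1.064 |

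In the first row the literal reading is off by 1.086 − 0.996 = 0.090, mITT agrees with it, and earlier scores remove the bias. In the second row mITT is off by 0.139 and the literal reading by 0.134. Earlier scores halve the error to 0.069 but do not remove it. With 10% Engensis and 20% Placebo missing, the second-row error changes sign (full −0.998, earlier scores −0.927). With 10% missing in both arms and the same mechanism, all methods agree to about 0.005. The R² for Day 365 is 0.16 from baseline alone (0.4²) and 0.62 with the earlier visits.

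**5. Wider grid with weaker dropout.** SD 2.0–2.4, correlation 0.6–0.8, slope 0.1–0.3 logit per point, dropout split before and after Day 270, repeated-measures fit. Absolute bias at the centre (SD 2.2, correlation 0.7, slope 0.2), with the grid range in brackets:

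| Case | Rate and mechanism matched | 15% vs 25% missing | 20% missing, pain-driven in one arm only |
|---|---|---|---|
| Earlier scores used; dropout on unseen Day 365 pain | at most 0.005 | 0.044 (0.01–0.09) | 0.080 (0.02–0.19) |
| Literal list; dropout on last observed pain | at most 0.008 | 0.054 (0.02–0.11) | 0.112 (0.04–0.22) |

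In the last column the other arm loses the same share completely at random. mITT bias in the first row's unmatched cases is 0.03–0.14 and 0.06–0.29, with the same sign as the primary. In the second row mITT is within 0.002 of the literal-reading bias. HbA1c, gender and age were not simulated, and neither was PP.

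**The case against.** **mITT is a different assumption.** A reader might infer that nothing in the plan varies the handling of missing data. That goes too far. A completer analysis rests on its own, usually stronger, assumption. If Step 2 uses earlier scores, mITT is more biased than the primary (0.03–0.14 against 0.01–0.09 at 15% vs 25%), so a gap between them carries some information. This stands, and it is why agreement is called weak evidence and not worthless. Near-identity of the two arises only under the literal Step 2 reading. Nor can PP be said to err in the same direction: it adds full dosing and eligibility review, and it was not simulated.

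**Earlier scores may already be intended.** A reader might infer that Step 2 excludes them. The text does not say that. A monotone pattern serves little purpose unless earlier visits are used, and a mixed model could bring them in. The documents support not named, and no more.

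**The sizes need dropout that differs by arm.** Follow-up is blinded, without dosing and on one schedule, and the documents give no arm-specific reason to stop. A 15% vs 25% split needs a logit gap of 0.64; slopes of 0.1–0.3 acting on a 1-point difference supply only 0.1–0.3. With one common pain-driven mechanism, earlier scores used and 20% Placebo missing, simulated bias was 0.002–0.030, towards a smaller Engensis benefit. At 30% it reached 0.049. This stands: the larger figures are possible, not expected.

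**The plan limits missing data.** Diary data count when a visit is missed (SAP 10.3), visits are rescheduled, ITT begins at Day 180, average pain is recorded daily, and the full BPI-DPN is sought at early termination. Returning pain may thus be recorded before the diary stops. But SAP 10.6 still expects early withdrawal, and 10.6.1 does not say that these scores inform the imputation.

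**Another analysis may exist.** SAP 12.0 points to Sections 8.4.2 and 8.4.4, and the abbreviation list carries MOTH (mean of the other group). A reader might infer a dropped or hidden analysis. The pointer looks like stale numbering, as in 12.2 and 12.5.2.1. MOTH is used nowhere visible. By the table of contents, the redaction after 12.5.3 covers exploratory endpoints, and 12.5.1.1 shows no redaction. Neither trace supplies the missing run or proves that one was removed.

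**Conclusion.** The point holds in a limited form. The primary Day 365 comparison assumes missing at random, and no visible planned run tests departures from that assumption for the participants whose scores are missing. mITT and PP are Day 365 completer analyses, and their agreement with ITT would be weak support. Step 2 needs clarifying: read literally it can bias the result, and mITT would not show it.

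The size is conditional on assumed inputs. It is about zero (0.01 or less) when missing rate and mechanism match between arms, and roughly 0.04–0.11 points in the central unmatched cases. A reader might take these as the bias to expect in this trial; without N, SD or dropout rates the documents do not support that. What can be said is that neither small nor large bias can be ruled out from the plan, and that a tipping-point analysis would report how much departure the conclusion tolerates. The change is worth making; confidence is medium.

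**What to change.** Amend the SAP before database lock and unmasking.

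1. **Section 10.6.1.** State that missing ADPSs are imputed by arm from all available post-baseline ADPSs (Days 90, 180 and 270) plus the four listed factors, by sequential monotone regression or by a mixed model with within-subject correlation.
2. **Section 12.5.1.1.** Add an ITT delta-adjusted tipping-point analysis using the same 10-dataset procedure.
   - Apply delta only to monotone (dropout) imputations at Day 270 and Day 365, not to intermittent gaps filled in Step 1. Otherwise it would shift a Day 270 gap in someone whose Day 365 mean was observed.
   - Use 0.5-point steps and keep scores within 0–10.
   - Worsen Engensis alone as the main stress test, and vary the Placebo delta as well so that both directions are covered.
   - Report the estimate, 95% CI and p-value at each step, and the crossing delta if there is one.
3. **Sections 9.3, 9.4 and 12.5.1.1.** Describe mITT and PP as Day 365 completer analyses.

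Cost: SAP wording, a loop around the planned imputation and pooling code, and one table. Data collection does not change. The result may look less robust than it would without the analysis.

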12.5.2 Analysis of the Secondary Efficacy Endpoints

12.5.2.1 Change from Baseline in the means of Worst Pain Scores at Day 365 Visit

The change from Baseline (Study VMDN-003-2) in mean worst pain score at the Day 365 visit will be analyzed using the same linear mixed method described in Section 8.4.1 for the ITT population. Missing data will be handled according to the method pre-specified in [Section 12.5.1](#)

12.5.2.2 Proportion of Responders (≥50% reduction in mean ADPS) on Day 365

Responders will be defined as participants with at least 50% reduction from Baseline in the mean ADPS at the Day 365 visit. The percent reduction will be computed as follows:

$$\%Change = \frac{Day\ 365\ mean\ ADPS - Baseline\ mean\ ADPS}{Baseline\ mean\ ADPS} \times 100$$

For each 10 completed datasets imputed using the MI method, a generalized linear mixed-effects model for repeated measures based on a logit link function (hereinafter, the categorical Repeated Measures Model) will be used for comparing the percentage of responders between the two study treatment groups. The model will include treatment, visit, treatment-by-visit interaction, and baseline (Study VMDN-003-2) Average Daily Pain Score as covariates with an unstructured variance-covariance matrix. Then the Proc MIANALYZE procedures will be used to generate the point estimate and the corresponding 95% confidence interval. Study visits from main study will include Baseline and Day 180 and extension study Day 270 and Day 365 will be included.

The SAS code to be used to conduct the analysis is presented below:

```
PROC GLIMMIX DATA=work method=REML;
class usubjid trtp avisitn;
MODEL critvar(event='Y') = trtp base avisitn trtp*avisitn / DIST=binary LINK=LOGIT SOLUTION;
random INTERCEPT / SUBJECT=usubjid type=un;
lsmeans trtp *avisitn / diff cl; RUN;
```

where

USUBJID: subject ID TRTP: treatment

AVISITN: variable representing visits

CHG: change in Average Daily Pain Score from baseline(Study VMDN-003-2)

BASE: (Study VMDN-003-2) Average Daily Pain Score (continuous variable)

CRITVAR: a Y/N variable indicating if the participant had at least a 50% reduction in Average Daily Pain Score from baseline (Study VMDN-003-2) at that visit

Other variance-covariance structures selected from among compound symmetry, Toeplitz, and autoregressive (1) options will be substituted based on the lowest AIC if convergence problems arise.

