9.3.2. Secondary Endpoints

The secondary efficacy endpoints include the following:

- Change in the means of the Worst Pain scores from the full BPI-DPN from the 7 days prior to the Day 0 Visit (Study VMDN 003 2) to the 7 days prior to the Day 270 Visit and the 7 days prior to the Day 365 Visit for Engensis compared to Placebo
- Proportion of Responders (≥ 50% reduction in the ADPSs from the full BPI-DPN) from the 7 days prior to the Day 0 Visit (Study VMDN-003-2) to the 7 days prior to the Day 270 Visit and the 7 days prior to the Day 365 Visit for Engensis compared to Placebo

Secondary safety endpoints include:

- Incidence of TEAEs and TESAEs for Engensis compared to Placebo
- Incidence of clinically significant laboratory values for Engensis compared to Placebo

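### The responder model is meant to compare percentages, but its code yields a subject-specific log-odds difference, and no between-arm percentage difference with a confidence interval is specified.

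*SAP*

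**What the plan says.** Protocol 9.3.2 lists as a secondary efficacy endpoint the "Proportion of Responders (≥ 50% reduction in the ADPSs from the full BPI-DPN"), from the week before Day 0 to the weeks before Day 270 and Day 365, Engensis against Placebo. It is a proportion in each arm.

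SAP 12.5.2.2 analyses it with "a generalized linear mixed-effects model for repeated measures based on a logit link function", which "will be used for comparing the percentage of responders between the two study treatment groups". The text describes treatment, visit, their interaction and baseline ADPS "as covariates with an unstructured variance-covariance matrix". The code reads:

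- "PROC GLIMMIX DATA=work method=REML"
- "MODEL critvar(event='Y') = trtp base avisitn trtp*avisitn / DIST=binary LINK=LOGIT SOLUTION"
- "random INTERCEPT / SUBJECT=usubjid type=un"
- "lsmeans trtp *avisitn / diff cl; RUN"

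MIANALYZE then gives a point estimate and 95% CI over ten datasets. The section does not name the scale of that estimate.

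Elsewhere, SAP 12.0 has categorical variables summarised by counts and percentages, and SAP 12.5.3 adds frequencies and percentages by arm and visit within subgroups. Neither section gives a between-arm difference with an interval.

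**The concern.** The stated aim and the coded output are different quantities. With a participant random intercept on the logit scale, the LS-means difference compares log-odds at the same value of the participant effect. The endpoint compares the share of responders in two groups of people. The logit link is non-linear, so one does not convert into the other by back-transformation. When the intercept variance is above zero and there is an effect, the conditional odds ratio lies further from 1 than the population odds ratio.

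This is the only inferential analysis of the responder endpoint. SAP 12.5.2.3 and 12.5.3 carry the secondary-endpoint analyses into the mITT, PP and subgroup sets. At stake is how the size of the effect is reported and read. A reader told that percentages were compared may take the pooled figure, or rates derived from it, as describing the participants.

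**Working it through.** **Inputs from the documents.** The model, link, random intercept, contrast and estimation option come from SAP 12.5.2.2. The documents give no responder rate, odds ratio, between-visit correlation, intercept variance or fixed sample size, so the plan has no figure of its own to reproduce. Everything numerical below is an assumption, shown over a range.

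**Step 1: what the contrast estimates.** Leaving out the baseline covariate, the coded model at one visit is logit P(response | u) = a_k + u, with u ~ N(0, s²), for arm k. The LS-means difference is a_1 − a_0, so the conditional odds ratio is exp(a_1 − a_0). The responder percentage in arm k is p_k = ∫ expit(a_k + u) φ(u; 0, s²) du. The latent between-visit correlation is r = s² / (s² + π²/3), so s = √[(π²/3) · r/(1 − r)].

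**Step 2: exact integral.** Assume p_0 = 25% and p_1 = 35%. The difference is 10 points and the marginal odds ratio is (0.35/0.65)/(0.25/0.75) = 1.62. For each s, solve for a_0 and a_1 by Gauss-Hermite integration. At r = 0.5, s = 1.81, a_0 = −1.686 and a_1 = −0.961, so the conditional odds ratio is exp(0.725) = 2.07 (to rounding). Back-transforming at u = 0 gives expit(−1.686) = 15.6% and expit(−0.961) = 27.7%.

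| Latent correlation r | Intercept SD s | Conditional OR (marginal 1.62) | Back-transformed rates at u = 0 (true 25% v 35%) |
|---|---|---|---|
| 0.07 | 0.50 | about 1.65 | 23.9% v 34.2% |
| 0.3 | 1.19 | 1.82 | 19.9% v 31.2% |
| 0.5 | 1.81 | 2.07 | 15.6% v 27.7% |
| 0.6 | 2.22 | 2.26 | 13.0% v 25.3% |
| 0.7 | 2.77 | 2.58 | 9.9% v 22.1% |
| 0.8 | 3.63 | 3.22 | 6.2% v 17.4% |

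Other assumed rates behave alike. For 30% v 40% (marginal 1.56) the conditional odds ratio is 1.59, 1.70, 2.05 and 2.57 at s = 0.5, 1, 2 and 3. For 20% v 30% (marginal 1.71) it is 1.76, 1.88, 2.33 and 3.02.

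**Step 3: the null.** With 30% in both arms, the conditional odds ratio is 1.00 at every s. The hypothesis being tested is the same on either scale.

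**Step 4: the coded estimation method.** The code says `method=REML` and requests no quadrature. If that means linearised restricted pseudo-likelihood (an assumption), the fitted value differs from the exact integral. Simulation with 6,000 per arm, three post-baseline visits and no baseline covariate gave:

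| Assumed rates | s | Observed marginal OR | Pseudo-likelihood OR | Full-likelihood OR |
|---|---|---|---|---|
| 30% v 40% | 1 | 1.53 | 1.54 | 1.65 |
| 30% v 40% | 2 | 1.54 | 1.63 | 2.02 |
| 30% v 40% | 3 | 1.54 | 1.69 | 2.60 |
| 30% v 45% | 1 | 2.03 | 2.07 | 2.34 |
| 30% v 45% | 2 | 1.83 | 1.98 | 2.69 |
| 30% v 45% | 3 | 1.92 | 2.22 | 4.12 |

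Pseudo-likelihood lies between 1.54/1.53 − 1 = 1% and 2.22/1.92 − 1 = 16% above the observed marginal odds ratio. The same model on the same data can thus give 1.69 or 2.60 depending on the approximation. Neither result is a difference in percentages.

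**The case against.** The strongest reply is that nothing here is biased. A conditional odds ratio is a legitimate estimand, the null is unchanged, the SAP promises neither an odds ratio nor back-transformed rates, and raw percentages per arm are already planned under SAP 12.0. Most of that stands. Three stronger readings that a reader might infer are not supported:

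- *The odds ratio is inflated.* It answers a different question from the marginal one. It misleads only if read as a comparison of percentages.
- *The gap is large.* That needs strong between-visit correlation and exact likelihood. The documents state no correlation. At the mild end the exact values nearly coincide, and under linearised estimation the gap may be small throughout.
- *The problem is independent of the mismatch between the text's unstructured matrix and the single intercept variance in the code.* If that mismatch were resolved with a residual-side structure across visits, as in the SAP 12.5.1 code, the model would be marginal and the subject-specific issue would go.

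The reply does not close the gap. A residual-side model would still leave the contrast on the logit scale. The raw percentages come with no interval for their difference and no rule for combining them over ten imputed datasets. The scale of the pooled estimate remains unnamed.

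**Conclusion.** The point holds as a mismatch between stated target and estimate for one secondary endpoint. As coded, SAP 12.5.2.2 delivers a subject-specific log-odds difference and specifies no between-arm percentage difference with a CI. The validity of the test is not in question.

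The size is unknown. Under exact likelihood with assumed rates of 25% v 35%, the conditional odds ratio is from about 1.65 to 3.22 against a marginal 1.62, for latent correlations of 0.07 to 0.8. Under linearised pseudo-likelihood, in the scenarios simulated, it is about 1% to 16% above the marginal value. All of this rests on assumed rates, a normal random intercept and no baseline covariate. The finding itself rests only on the SAP's text and code.

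**What to change.** Make the between-arm difference in responder percentage the reported estimate at Day 365 and at Day 270, the two time points in Protocol 9.3.2. In each imputed dataset:

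1. Fit a logistic regression at that visit with treatment and baseline ADPS.
2. Predict each ITT participant's risk under Engensis and under Placebo, and average within each.
3. Take the two percentages and their difference, with delta-method standard errors.
4. Pool all three in MIANALYZE and report 95% CIs.

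The imputed datasets are complete, so the per-visit model should lose little or no information on the contrast.

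If the mixed-model odds ratio is kept, label it conditional and supportive, and state how it is estimated (linearisation, Laplace or quadrature). A marginal model, such as GEE or a residual-side structure, is a reasonable alternative to the random intercept, but it too needs a step that turns the logit contrast into a percentage difference.

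The cost is one paragraph, one SAS block and one more reported estimate. No data collection or sample size changes.
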